## **2. Study design:**

Single arm, prospective unblinded study on post Watchman LAA closure device implant anti-coagulation management at a primary center (Vanderbilt Medical Center) and up to 5 additional high volume LAA implant centers. This trial will be designed to evaluate the use of dabigatran for 90 days post implantation of an LAA closure device (Watchman LAA Closure Device, Boston Scientific Inc.). The drug will be initiated on the morning following device implantation, taken BID per package insert dosing and until follow-up 90-day post implant TEE. Aspirin monotherapy will be utilized in conjunction at 81 mg for up to 12 months, after which the patients will be exited from the study and further treatment decisions will be made by the following physician (see Schedule of Study Procedures at end of protocol). The objective of this trial is to evaluate safety and efficacy of a 90-day period of dabigatran etexilate following LAA closure to prevent device associated thrombus, while minimizing adverse bleeding by eliminating the need for clopidogrel. This is a single arm pilot study with the option (pending collaboration with additional funding source) to expand to a full single arm non-inferiority trial design with 80% power to detect a 1.4% difference with the non-inferiority margin 1% in absolute rate of DAT (control rate 3.9%).

Prospective, non-randomized single arm study. Comparison will be made to historical controls based on published one year DAT rates from PROTECT-AF, PREVAIL clinical trials, and EWOLUTION, and ACP/Amulet registries.

Echocardiography (TEE) will be performed at 90 days (3 months, +/- 2-week window), and again at 1-year post implant (+/- 4 weeks). Selected images will be interpreted by echo lab at coordinating center in an anonymous fashion (patient data de-identified). Ideal imaging will incorporate 0, 45, 90 and 135 degree angled views on the device at follow up.

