Dosing regimen of dabigatran will be by FDA and pharmacokinetic labeling for dabigatran 150mg BID dosing if Creatinine clearance >30mL/min, and 75mg BID dosing if 15-30mL/min. This will be based on calculated CC by baseline labs performed on day of implant. Additional dosing adjustments per package insert for patients taking dronedarone 400mg BID, or ketoconazole will be made consistent with drug label. The majority of subjects will be expected to be on 150 mg BID for 90 days. Subjects on 75 mg twice daily dosing may be enrolled if renal function is stable in the range of 15-30mL/min. Aspirin 81 mg a day will be taken along with oral anticoagulation for 90 days followed by longer-term aspirin 81 mg daily aspirin dose. At the 90 days TEE follow up (3 months) a PCV or CBC will be drawn and compared to baseline PCV pre-LAA closure implant as an assessment of

indolent blood loss (there is expected intra-procedural blood loss from back bleed on access sheaths estimated 25-125mL).

Drug required for study: Initially start with 100 subject pilot study on therapy for 90 days, with option to expand to full non-inferiority study if collaborative funding is secured (IF study expands beyond pilot, estimate 262 subjects, 90 days on therapy). Estimate 80% or more subjects on 150mg BID dosing, and up to 20% subjects on 75mg BID dosing. With either the 100-subject pilot study, or optional expanded single arm study (262 patients) the objective is to establish a device associated thrombus (DAT) rate at 3 months and 1 year within 1.5% or less deviation from published DAT rates at 3.9% (Saw, J., et al). Comparison will be made to published data on Watchman LAA closure utilizing the 45-day warfarin after implant followed by six-month dual antiplatelet regimen, or registry data from European experience on Watchman and Amulet/ACP LAA closure systems.

Patients can be consented for the trial on the day of implantation or up to one month prior in clinic during consultation for LAA closure. This is an unblinded, single arm prospective study. Study exit visit will be coordinated with final twelve-month follow-up imaging after LAA closure implantation.

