### **Statistical Methods/Calculations:**

Statistical sample size calculation to establish comparable DAT rate with the prescribed regimen:

Available data for background on DAT;

Overall incidence of DAT was 3.9% (82 DAT for 2118 implanted devices)

Lempereur et al. Meta-Analysis [ref 19]: 30 studies describing DAT events were included in the analysis. The overall incidence of DAT was 3.9% (82 DAT for 2118 implanted devices). The median time from procedure to diagnosis of DAT was 1.5 months (IQR: 0-2.9). Most cases were diagnosed with transesophageal echocardiogram (TEE). The treatment consisted of low molecular weight heparin (LMWH) in 45.5% of cases, and oral anticoagulation (OAC) or other treatment modalities in 54.5%. Complete thrombus resolution was achieved in 95.0% of cases (100% with LMWH and 89.5% with OAC). Treatment duration varied greatly with a median treatment duration of 45 days (IQR: 14-

135). Clinical events related to DAT consisted of neurologic events namely two transient ischemic attacks (2.4%) and four ischemic strokes (4.9%).

Saw et al [ref 7]. 339 analyzable TEE in follow up. Patients' mean age was  $74.4 \pm 7.5$  years, and 67.3% were men. The mean CHADS2 score was  $2.7 \pm 1.3$ , the mean CHA2DS2-VASc score was  $4.3 \pm 1.5$ , and the mean HAS-BLED score was  $3.0 \pm 1.2$ . Peri-procedural major adverse events occurred in 2.4%. Median clinical follow-up duration was 355 days (range 179 to 622 days). Follow-up transesophageal echocardiography was performed after a median of 134 days (range 88 to 227 days). Device-associated thrombus was observed in 3.2% Independent predictors of device-associated thrombus were smoking (odds ratio: 5.79;  $p = 0.017$ ) and female sex (odds ratio: 4.22;  $p = 0.027$ ).

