Kaneko et al. [ref 20] 78 patients (50 males,  $72 \pm 8$  years, average CHA2DS2-VASc score of  $4.3 + 1.8$ ) who had undergone WATCHMAN implantation. WATCHMAN was successfully implanted in all patients and four (5%) developed DRT. Patients with DRT were more often female (75 vs. 34%,  $p = 0.094$ ). CHA2DS2-VASc score was higher for patients with DRT ( $6.3 \pm 2.5$  vs.  $4.2 \pm 1.7$ ,  $p = 0.022$ ). Chronic kidney disease (100% vs. 43%,  $p = 0.024$ ) and deep implantation of the device, which was defined as implant position below the LAA ostial plane (75 vs. 24%,  $p = 0.026$ ), were more common in patients with DRT. HAS-BLED score ( $4.5 \pm 1.0$  vs.  $3.5 \pm 1.1$ ,  $p = 0.074$ ) was higher and oral anticoagulants (50 vs. 84%,  $p = 0.086$ ) were less commonly prescribed for patients with DRT. Multivariable logistic regression analysis showed that higher CHA2DS2-VASc score ( $p = 0.022$ , OR 2.8) and deep implantation ( $p = 0.032$ , OR 24.7) were associated with DRT. These results suggest the possible role of CHA2DS2-VASc scores and implantation depth in the development of DRT after percutaneous LAA closure using the WATCHMAN device.

With a single arm non-inferiority trial design to show the absolute rate of DAT is less than the control rate of 3.9% by a non-inferiority margin of 1% having a power 80% to detect a 1.4% difference at 0.05 level of significance, we would need 262 total subjects enrolled and reaching imaging endpoint evaluation. The initial study will begin with pilot to 100 subjects (with 46% power) with an option to expand if additional funding source is obtained.

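### The 80% power at 262 subjects and 46% at 100 rest on a large-sample formula that fails at 2 to 7 expected events; tests at or near one-sided 5% give about 52–67% and 28%

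*Combined protocol and SAP*

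**What the plan says.** Statistical Methods/Calculations describes a single-arm non-inferiority design meant to "show the absolute rate of DAT is less than the control rate of 3.9% by a non-inferiority margin of 1" percent. For the optional expansion it states: "having a power 80% to detect a 1.4% difference at 0.05 level of significance, we would need 262 total subjects". It then starts with a "pilot to 100 subjects (with 46% power").

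Section 2, Study design, repeats the claim for the expansion: "80% power to detect a 1.4% difference with the non-inferiority margin 1% in absolute rate of DAT (control rate 3.9" percent). The drug-supply paragraph after the exclusion criteria repeats the size: "IF study expands beyond pilot, estimate 262 subjects, 90 days on therapy".

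The control rate comes from a meta-analysis: "Overall incidence of DAT was 3.9% (82 DAT for 2118 implanted devices"). The primary endpoint is DAT on one-year imaging, a yes/no outcome. No test, confidence interval method, sidedness or maximum event count for success is given anywhere.

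**The concern.** DAT is rare, and at these sample sizes the result turns on a handful of events. A normal approximation can be badly wrong in that range, particularly when its variance is taken only at the hoped-for rate and not at the non-inferiority bound. If the stated power comes from such a formula, one of two things follows. With a test that holds its 5% level, the expansion is much weaker than stated. With a test that delivers roughly the stated power, non-inferiority is declared wrongly more often than stated.

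The 80% figure is what a funder would rely on when deciding whether to pay for the expansion. Because no test or event limit is fixed, 7 or 8 events in 262 could be called success or failure after the data are seen.

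**Working it through.** **Inputs**
- Control rate 3.9% (82/2118 = 3.87%), from Statistical Methods/Calculations.
- Margin 1% absolute, from the same section and Section 2. Inferred bound: 3.9 + 1 = 4.9%.
- Difference to detect 1.4%. Inferred true rate: 3.9 − 1.4 = 2.5%.
- Level 0.05, sidedness not stated. Inferred: one-sided.
- Distance from bound to true rate: 4.9 − 2.5 = 2.4 points.

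**Step 1: reproduce the plan's figures.** One-sample normal formula, variance at the alternative only:

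- n = (1.645 + 0.842)² × 0.025 × 0.975 / 0.024² = 261.6, so 262.
- Power at 100 = Φ(0.024 × √100 / √0.024375 − 1.645) = 45.7%, so 46%.

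Both stated figures match.

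**Step 2: other readings.** None of those tried gives 262.

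| Reading | n for 80% power |
|---|---|
| Same formula, two-sided 0.05 | 333 |
| One-sided, null variance only | 501 |
| One-sided, null variance for the test and alternative variance for power | 411 |
| As above, two-sided | 534 |
| Bound 3.9% (plain superiority), true rate 2.5% | 769 |
| Bound 4.9%, true rate 3.9% | 2,318 |
| Bound 2.9% (literal wording), true rate 2.5% | 9,419 |

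**Step 3: is the approximation sound?** Expected events at 2.5% are 262 × 0.025 = 6.55 and 100 × 0.025 = 2.5. The variance used is 0.025 × 0.975 = 0.0244. At the bound it is 0.049 × 0.951 = 0.0466, almost twice as large. Putting the null variance in the test alone lowers the formula's power at 262 to 58.5%.

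**Step 4: binomial size and power.** Each rule declares non-inferiority if the DAT count is at most c. Size is P(X ≤ c) at 4.9%; power is P(X ≤ c) at 2.5%.

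| n | Test | c | True alpha | Power |
|---|---|---|---|---|
| 262 | Exact | 6 | 2.6% | 51.8% |
| 262 | Randomised exact, size exactly 5% | 6 or 7 | 5.0% | 64.3% |
| 262 | Score, mid-p | 7 | 5.4% | 66.6% |
| 262 | Wald (matches the formula) | 8 | 10.2% | 78.8% |
| 100 | Exact, score, mid-p | 1 | 4.0% | 28.3% |
| 100 | Wald | 2 | 12.7% | 54.2% |

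The randomised test is the most powerful 5% test for this one-sided binomial problem. No test that holds 5% can therefore exceed 64.3% at 262.

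**Step 5: is 262 just an unlucky size?** Partly. Exact power moves in a sawtooth, and 262 is a low point: 266 subjects allow 7 events (alpha 4.9%) and give 65.1%. But for every n from 230 to 290, exact power lies between 45% and 65%. It first reaches 80% at n = 394 (at most 12 events, 80.8%) and stays there from 443.

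**Step 6: sensitivity**
- If 0.05 is two-sided, the plan's own formula gives 70% at 262 and 34% at 100. Exact tests at one-sided 0.025 give 36% (at most 5 events) and 8% (0 events).
- If the true rate equals the control rate of 3.9%, exact power at 262 is 11%.

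**The case against.** The strongest reply is that the plan's arithmetic is not mistaken. Under the Wald rule that matches its formula, true power at 262 is 78.8%, close to the stated 80%, and at 100 it is 54.2%, above the stated 46%. What fails under that rule is the error rate, not the power. This is correct, but it does not rescue the claim. The plan ties its power to the 0.05 level, and the Wald rule runs at 10.2% and 12.7%. It does mean that calling 46% too high is true only for tests near 5%.

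Second, the drug-supply paragraph gives a different tolerance: within 1.5% of the published 3.9%. If that means an upper bound of 5.4% (an assumption), 8 events in 262 would have alpha 5.3% and power 78.8%. But the plan's formula with that bound gives about 179 subjects, (1.645 + 0.842)² × 0.024375 / 0.029², not 262. It is also not the margin stated in the other two places. The inconsistency is real and should be removed along with the power figures.

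Third, the 262-subject study is only an option that depends on funding, and the pilot openly reports low power. That bears on urgency: no pilot procedure changes. It does not make the 80% correct, and that figure is the only power justification offered for the expansion.

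Finally, the choice of an exact test is a preference. That is fair. Score and mid-p tests are reasonable if named in advance with their true alpha, but they do not reach 80% either.

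**Conclusion.** The concern holds. At a 2.5% true rate against a 4.9% bound, tests at or near one-sided 5% have about 52–67% power at 262, not 80%, and about 28% at 100, not 46%. Keeping alpha at or below 5% with an ordinary exact test gives 51.8% at 262. The rule that roughly delivers the stated 80% has about twice the stated false non-inferiority rate.

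The conclusion rests on three inferred inputs: the 4.9% bound, the 2.5% true rate and one-sided alpha. The plan's wording is ambiguous, but of the readings tried only this one gives both 262 and 46%. A two-sided level makes the shortfall larger. The statement needs correcting before the expansion is funded or planned; the pilot can run as designed.

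**What to change.** Replace the sample-size sentences in Statistical Methods/Calculations with text such as:

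> H0: one-year DAT rate ≥ 4.9% (3.9% plus a 1% margin), one-sided alpha 0.05. Non-inferiority is shown if the one-sided 95% exact (Clopper-Pearson) upper bound, computed on subjects with one-year imaging, is below 4.9% (at most 6 events if exactly 262 are imaged). With 262 imaged and a true rate of 2.5%, power is about 52%. The 100-subject pilot will report the DAT rate with a two-sided 95% exact confidence interval and no pass/fail rule.

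The event limit follows from the upper bounds: 6/262 gives 4.47% and 7/262 gives 4.96%. For the pilot, 3 events in 100 would give an interval of 0.6% to 8.5%.

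- Delete the 46%, or restate it as 28%.
- Make Section 2 match, and reconcile the 1.5% tolerance in the drug-supply paragraph with the 1% margin.
- If a score or mid-p test is preferred, name it in advance and state about 67% power with a true alpha of 5.4%.
- If another bound or a two-sided level was intended, state it and recompute.
- Do not present 262 as giving 80% power when the expansion is planned.

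**Cost.** Text changes only, with no change to the pilot. The stated power becomes less favourable. Keeping 80% with the exact test takes 394 to 443 imaged subjects, which is 50% to 69% more than 262 (394/262 = 1.50; 443/262 = 1.69).

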## **1. Background and Study Rationale:**

Two years after FDA approval of the first left atrial appendage (LAA) closure device for the prevention of embolic stroke in patients with non-valvular atrial fibrillation, over 13,000 Watchman (Boston Scientific, Inc., Natick, MA) devices have been successfully implanted in the US. Post-approval prospective registry data in 3,822 consecutive cases demonstrated implantation was successful in 3,653 (95.6%), with a median procedure time of 50 min with the majority of operators new to the procedure (71%). Complications included 39 pericardial tamponades (1.02%), 3 procedure-related strokes (0.078%); 9 device embolizations (0.24%), and 3 procedure-related deaths (0.078%) [1]. The early phase PROTECT-AF complications topped 10%, but clearly as expertise in trans-septal access, and improvements in the delivery system and technique have evolved, total complications post implant have dropped to <3% in the EWOLUTION registry [2].

With proper patient selection, routine use of ultrasound to guide venous access, and a continued trend to implant without bridging anti-coagulation, expert centers may be able to reduce total acute complications below 1%. As a stroke prevention strategy, this could position LAA closure as a cost-effective consideration, potentially as first line therapy for many patients. Several landmark clinical trials are ongoing in the LAA occlusion space and will provide prospective randomized trial data on over 5000 patients closed with a variety of methods. The Amulet (Abbott Medical, Inc.) versus Watchman IDE clinical trial (clinical trials.gov # NCT02879448) has rapidly enrolled since opening in 2017 with a target enrollment of 1400 subjects and 300 roll-in cases. Subjects eligible for a Watchman LAA closure device are randomized 1:1 to Amulet or Watchman and followed for a minimum of 18 months for the endpoint of stroke or systemic embolism. Additionally, the surgical LAAOS-III trial is studying over 4000 patients undergoing open heart surgery with a history of AF, and randomized 1:1 to LAA excision, or no intervention on the LAA.

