### **Study duration and timelines:**

From completion of the protocol, approval of contract and site initiation at Vanderbilt University Medical Center, study duration would be as follows: Estimated rate of enrollment is 2-3 subjects per site per month. Estimated time to complete enrollment of 100

subjects is 12 months once all sites are open, followed by 1 year of follow up to reach 1 year post implant imaging. Estimate completion of study in 24 months.

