**Schedule of Study Procedures:**

	Baseline Visit	Procedure Day (+/- 3 days)	POD 1	90 Days Post Procedure (+/- 14 days)	1 Year Post Procedure (+/- 14 days)	AE/Other (e.g, DAT, study medication continued beyond 90 days)
Demographics	X					
H and P (including vital signs, height and weight)	X	X		X	X	X
I/E criteria (confirm eligibility)	X	X				
Informed Consent (a)	X	X				
CBC/BMP		X	X	X	X	X
Creat Cl	X	X	X	X	X	X
AE review	X	X	X	X	X	X
TEE		X (intra-operative)		X	X	X
Dispense Study Medication			X			X (as needed)
Pill Count/medication termination (planned)				X		X (as needed)
Exit					X	

(a) Informed Consent may be completed anytime up to one month prior to implant.

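### The 262 and 100 behind the stated 80% and 46% power are counts of imaged subjects, but the plan also uses them as the numbers treated and enrolled, with no allowance for loss before the 1-year image

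*Combined protocol and SAP*

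**What the plan says.** The last paragraph of Statistical Methods/Calculations tests whether "the absolute rate of DAT is less than the control rate of 3.9"%, with a 1% margin, 80% power for a 1.4% difference and a 0.05 significance level. It concludes that "we would need 262 total subjects enrolled and reaching imaging endpoint evaluation". It gives the pilot of 100 a power of 46%.

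The drug-supply paragraph at the end of the Inclusion and Exclusion Criteria section uses the same numbers for subjects on treatment: 100 in the pilot and, for the option, "IF study expands beyond pilot, estimate 262 subjects, 90 days on therapy". Study duration and timelines uses the pilot number as the recruitment target ("Estimated time to complete enrollment of 100" subjects, put at 12 months).

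The order of events is consent, implant, first dabigatran dose the next morning, TEE at 90 days, and TEE (or CT angiography) at 1 year for the primary endpoint. The schedule's footnote says "Informed Consent may be completed anytime up to one month prior to implant". No section states an expected loss, an analysis set, a denominator for the DAT rate, or a rule for a missing 1-year image.

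**The concern.** One number is used for three stages: enrolled, treated for 90 days, and imaged at 1 year. These agree only if nobody dies, withdraws or misses the image in the year after implant. If anyone does, the power actually available is below the stated figure, both in the pilot that is committed and in the optional expansion.

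The basis of the DAT rate is also left open. The 3.9% benchmark is 82 events over 2118 implanted devices, while another cited series, with 3.2%, reports 339 analyzable follow-up TEEs. With so few events expected, the choice between imaged and implanted subjects, and the treatment of missing images, can visibly move the estimate that is set against these benchmarks.

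**Working it through.** **Inputs.** From Statistical Methods/Calculations: control rate 3.9%, margin 1% (limit p0 = 4.9%), difference 1.4% (true rate p1 = 3.9% − 1.4% = 2.5%), significance level 0.05, power 80%. Sidedness is not stated. Loss between first dose and 1-year image: not in the documents, so 5% to 20% is assumed.

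**Reproducing the plan.** One-sample normal approximation, one-sided, with the variance at p1:

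n = (z₀.₉₅ + z₀.₈₀)² × p1(1 − p1) / (p0 − p1)² = (1.645 + 0.842)² × 0.025 × 0.975 / 0.024² = 261.6, rounded up to 262.

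Power(n) = Φ(0.024√n / √(0.025 × 0.975) − 1.645), which gives 80.0% at 262 and 45.7% at 100 (stated: 46%). With the same rates, a two-sided level would give 333, and taking the variance at the limit would give 501. So the plan used the form above, and 262 is the result before any allowance for loss.

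**Counting from the first dose.** Imaged = treated × (1 − loss), rounded down.

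| Assumed loss | 262 treated: imaged | Power | 100 treated: imaged | Power |
|---|---|---|---|---|
| 0% | 262 | 80.0% | 100 | 45.7% |
| 5% | 248 | 78.1% | 95 | 44.2% |
| 10% | 235 | 76.2% | 90 | 42.6% |
| 15% | 222 | 74.1% | 85 | 41.0% |
| 20% | 209 | 71.8% | 80 | 39.4% |

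**Counting from consent.** The Background cites a post-approval registry with 3,653 successful implants in 3,822 cases (95.6%). Applying it before the same losses gives 237 to 200 imaged of 262 (76.5% to 70.2%) and 90 to 76 of 100 (42.6% to 38.0%), a further 1 to 2 points lower.

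**Denominator, by illustration.** Suppose 100 are implanted and dosed, 85 are imaged and 2 have DAT. Per subject imaged: 2/85 = 2.4%. Per subject implanted and dosed: 2/100 = 2.0% if none of the 15 without an image had DAT, 3/100 = 3.0% if one did, and 17/100 = 17% if all did.

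All power figures use the plan's own approximation, to isolate the effect of loss. Whether that approximation suits so few events is a separate question.

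**The case against.** The sample-size sentence already asks for 262 who reach imaging, which is arithmetically right. That stands, and the problem is only that the other sections give no separate, larger number for subjects treated or enrolled. The plan also has features that limit loss: CT angiography for subjects who cannot have TEE, standard-of-care imaging at 1 year, a required life expectancy above one year, and exclusion of patients unable to attend follow-up. These make a small loss plausible but do not make it zero. Finally, 262 belongs to an unfunded option, and the pilot's power is openly low with no decision rule attached. That limits the consequences.

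Three stronger readings are tempting, and the documents do not support them.

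- *A reader might infer that 95.6% is the plan's own implant success and that enrolment slots are lost to it.* It is a cited registry result in which 71% of operators were new, whereas this study uses experienced centres, and the Watchman series of 78 patients in the statistical section reports no failed implant. Subjects failing the anatomy or platelet criteria were never eligible for enrolment. Implant failure also falls before the on-drug count.
- *A reader might infer that the plan removes leavers or early stoppers from the rate.* No section says so. The sentence on imaging is a sample-size statement, and the schedule does not make either TEE conditional on taking dabigatran.
- *A reader might infer that a rate among imaged subjects flatters the regimen.* The illustration shows that it can lie above or below the per-implant rate, so no direction is established.

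**Conclusion.** The point holds in a limited form. The stated 80% and 46% are reached only with no loss between first dose and 1-year imaging, while the plan treats and recruits exactly the numbers that it needs to image. Under an assumed 5% to 20% loss, power is about 78% to 72% for 262 treated and about 44% to 39% for 100 treated. Counting from consent takes off a further 1 to 2 points if the registry's implant success applies. The size rests on the assumed loss and on the plan's approximation; the direction does not depend on the loss chosen. The denominator and the handling of missing images are undefined, which is a gap in the text and not evidence of bias.

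**What to change.** 1. In Statistical Methods/Calculations, label 262 and 100 as subjects with 1-year imaging wherever they carry the 80% and 46%.
2. State an expected loss between first dose and the 1-year image, with its basis, and restate the power at the resulting evaluable number for the planned 100 and 262 treated. Enrolment need not rise.
3. Report the DAT rate both per subject imaged and per subject implanted and dosed, and say which basis is set against which published benchmark.
4. List the reasons for each missing 1-year image. Show the rate with those subjects counted as all without and all with thrombus. The upper bound will be wide (17% in the illustration), so present it as a range and not as a test.

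The cost is a few sentences and one table, with no added subjects or drug. The downside is that the stated power becomes slightly less favourable.
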